Appendix 17.1	Updated the escalation, de-escalation, and discontinuation rules to specify criteria related to the occurrence of worsening anemia. Under the revised criteria, subjects with a hemoglobin (HgB) < 9 g/dL will not be escalated to the next column size and subjects whose HgB decreases to < 9 g/dL at a given column size despite optimized ESA treatment will be de-escalated or discontinued as applicable.	Updated to account for monitoring of anemia and to provide enhanced clarity concerning escalation, de-escalation, and discontinuation rules.
Appendix 17.2	Appendix was eliminated.	Duplicative content was removed for clarity.

Protocol Version 1.2 dated 13NOV2019
Replaces: Protocol Version 1.0 dated 11OCT2019

The following table describes changes from Version 1.1 (dated 11OCT2019) with justifications provided.

Section(s)	Description	Justification
Throughout	Protocol version update. Previously read: V1.1_11OCT2019 Now reads: V1.2_13NOV2019	Version control.
Throughout	Minor grammar and content updates.	Minor grammar/content updates for clarity/accuracy of content.
Table of Contents	Minor content updates.	Minor updates required to reflect revised content.
List of Abbreviations	Minor content updates.	Minor updates required to reflect revised content.
6.1.2.1	Content revised to remove term “control device” and replace with “control” only.	Revised to prevent confusion regarding control.
6.2, 15.1.2, 15.1.3, 15.1.4, 15.1.5	Control accountability added to heading (6.2) and content of sections.	Revised to include accountability for control.
8	The following sentence was added, “When assessing relatedness, it should be assumed the subject was randomized to the AKST1210 column unless unblinding is required.”	Revisions related to prevention of inadvertent unblinding.
8.1.2	Section removed and Section 8.1.3 renumbered to Section 8.1.2.	Device deficiencies and user errors will now be reported as technical errors.
8.2.1	Term “ADE” added to section.	Provide clarity regarding adverse event classification.
8.2.3	Heading changed to, “Expectedness of Adverse Device Effects.”	Provide clarity regarding section content.
8.2.3.1	Second paragraph revised to information regarding assessment and reporting of a UADE.	Provide clarity regarding UADE assessment and reporting.
8.3.1	Heading changed to “Post-Study Safety Assessment.”	Avoid use of abbreviations in heading per style guidelines.
8.4.1, 8.4.2	Extensive content revisions related to reporting procedures.	Revisions related to compliance with standard device protocols.
8.5	Refinement of content related to description of the “Safety Evaluation Meeting.”	Minor updates for clarity/accuracy of content.
12.2	Content updates related to written notification IRB/IEC withdrawal of approval.	Minor updates for clarity/accuracy of content.
12.3.2	The following sentence was removed, “It is required that	Duplication of content now

	written informed consent be obtained within 5 working days of the use of the investigational device.	provided in (new) Section 13.1.1.1.
13.1.1	Content updates related to investigator reporting responsibilities.	Revisions related to compliance with standard device protocols.

Protocol Version 1.1 dated 11OCT2019
Replaces: Protocol Version 1.0 dated 06SEP2019

The following table describes changes from Version 1.0 (dated 06SEP2019) with justifications provided.

Section(s)	Description	Justification
Throughout	Protocol version update. Previously read: V1.0_06SEP2019 Now reads: V1.1_11OCT2019	Version control.
Throughout	Minor grammar and content updates.	Minor grammar/content updates for clarity/accuracy of content.
Table of Contents	Minor content updates.	Minor updates required to reflect revised content.
List of Abbreviations	Added abbreviations related to device events.	Revisions related to compliance with standard device protocols.
Protocol Approval Page	Addition of 21 Code of Federal Regulations (CFR) 812, and International Organization for Standardization (ISO) 14155:2011.	Revisions related to compliance with standard device protocols.
Protocol Summary, 4.1, 5.3, 5.4.2, 10.5	Content added to indicate there will be approximately 26 subjects enrolled with the intent of obtaining 20 evaluable subjects (assuming a drop-out rate of 20%).	Revised subject enrollment to obtain appropriate number of evaluable subjects.
2.3.1	Content revised and extended to include detailed description of known potential risks for device (previously only included a cross-reference to the Investigator's Brochure).	Revisions related to compliance with standard device protocols
4.1	Clarification of maximum flow rate of 250 mL/minute, which increased overall length of dialysis time to approximately 4 hours.	Provide clarity regarding flow rate and extended length of dialysis.
5.5	Content added regarding Sponsor/investigator notification of IRB withdrawal.	Revisions related to compliance with standard device protocols.
6	Extensive content additions to fully describe device labeling, storage, escalation, and administration. A brief description of the control was also added.	Revisions related to compliance with standard device protocols.
7.1.1.1.6	Content revised for clarification of heparin regimen during Treatment Periods.	Provide clarity regarding heparin regimen.
7.1.1.1.8	Content revised for clarification of PHQ-9 administration.	Provide clarity regarding PHQ-9 administration.

8	Extensive content revisions related to safety parameters as well as device event descriptions, classifications, expectedness, reporting procedures, and study halting rules.	Revisions related to compliance with standard device protocols.
12, 13	Content updates related to reporting procedures, data handling, and record keeping that are specific to device trials.	Revisions related to compliance with standard device protocols.
15.2	Added Calcium (Total/Free) to serum chemistry.	Added for monitoring of calcium levels.

| APPENDIX A - PROGRAMMING SPECIFICATIONS FOR TABLES AND LISTINGS | | 38 |
| APPENDIX B – SCORING INSTRUCTIONS | | 40 |
| REFERENCES | | 49 |

1 Introduction

This Statistical Analysis Plan (SAP) describes the planned statistical analyses to be performed for data from Protocol AKST1210-201, “A Randomized, Double-Blind, Phase 2a Placebo-Controlled Study to Evaluate the Tolerability, Feasibility, and Efficacy of AKST1210 in Patients on Hemodialysis with Cognitive Impairment Associated with End-Stage Renal Disease”. This SAP was created using Clinical Protocol AKST1210-201 Version 2.1 dated 14FEB2020. Reference materials for this statistical plan include the protocol and the accompanying sample data collection documents. Operational aspects related to collection and timing of planned clinical assessments are not repeated in this SAP unless relevant to the analysis.

The structure and content of this SAP provides sufficient detail to meet the requirements identified by the Food and Drug Administration (FDA), European Medicines Agency (EMA), and International Conference on Harmonisation (ICH) of Technical Requirements for Pharmaceuticals for Human Use: Guidance on Statistical Principles in Clinical Trials (1998). All work planned and reported for this SAP will follow internationally accepted guidelines, published by the American Statistical Association (2016) and the Royal Statistical Society (2014) for statistical practice.

The planned analyses identified in this SAP may be included in clinical study reports (CSRs), regulatory submissions, or future manuscripts. In addition, post-hoc exploratory analyses not necessarily identified in this SAP may be performed to further examine study data. Any post-hoc or unplanned exploratory analysis performed will be clearly identified as such in the final CSR.

The statistical plan described hereafter is an *a priori* plan. It will be submitted to file prior to any unblinded inferential or descriptive analysis of data pertaining to Alkahest’s study AKST1210-201.

The table and listing shells will be provided in separate files as attachments to this SAP.

2 Study Objectives

2.1 Primary Objective

The primary objective is to assess the safety and tolerability of AKST1210 for the treatment of ESRD-CI in subjects receiving HD.

2.2 Secondary Objectives

The secondary objectives are to evaluate the feasibility of conducting expanded studies of AKST1210 in subjects with ESRD-CI who are undergoing HD 3 times per week as well as the efficacy of the column.

2.3 Exploratory Objectives

The exploratory objectives include serial compositional analysis of plasma to identify specific biomarkers possibly associated with cognitive function and/or indicators of

disease progression by proteomic analyses, magnitude of b2M removal, and possible relationship to changes in cognition.

3 Study Endpoints

3.1 Primary Endpoint

Incidence of treatment-emergent adverse events (TEAEs) and serious adverse events (SAEs) coded by the Medical Dictionary for Regulatory Activities (MedDRA) preferred term (PT) and grouped by MedDRA System Organ Class (SOC).

3.2 Secondary Endpoints

- Feasibility of all procedures, including blinding.
- Tolerability of each column size escalation, as measured by subject compliance with study visit schedule/completion, visit procedures, and subject retention.
- The change in IDH Rate above each subject's Historical IDH Rate for each column size.
- The incidence of IDH leading to de-escalation or discontinuation.
- The incidence of worsening anemia by column size.
- The incidence of anemia leading to de-escalation or discontinuation.
- Change from baseline in levels of b2M at Weeks 4, 8, 12 and end of study (EOS) and evaluation of any differences in the magnitude of change based on column size and duration of treatment with a specific column size.
- Change in Montreal Cognitive Assessment (MoCA) from baseline to EOS.
- Change in cognitive domains as measured with the Cogstate battery (i.e., verbal learning, psychomotor function, visual attention, working memory, executive function, and verbal delayed recall).
- Change in quality of life per the Short-Form Health Survey (SF-36).
- Change in the Patient Health Questionnaire-9 (PHQ-9).
- Change in sleep quality as measured by the Pittsburgh Sleep Quality Index (PSQI).
- Change in fatigue as measured by the Fatigue Questionnaire – Functional Assessments of Chronic Illness Therapy (FACIT).
- Changes from baseline in laboratory test data, vital sign measurements, and electrocardiograms (ECGs).

3.3 Exploratory Endpoints

- Serial compositional analysis of plasma to identify specific biomarkers associated with cognitive function and/or indicators of disease progression by proteomic analyses.
- Magnitude of b2M removal and possible relationship to changes in cognition.

4 Study Overview

4.1 Study Design

This will be a randomized, double-blind study conducted at up to 5 sites in the US. Approximately 26 male and female subjects, ≥ 40 years of age on HD with ESRD-CI, will be enrolled. Assuming a drop-out rate of 20%, enrollment at this level will yield approximately 20 evaluable subjects.

During Screening (Visit 1, Day -42 through Day -14), subjects and/or their legally authorized representative (LAR) will provide informed consent, and subjects will undergo screening assessments including provision of demographics and medical history, physical examination, 12-lead ECG, laboratory testing (including pregnancy testing if applicable), as well as tests to assess cognitive function and depression. A blood sample will also be obtained and sent to the site's local laboratory to determine baseline b2M concentration.

If the Visit 1 Screening eligibility criteria are met, subjects will commence the Run-in Period (Visits 1.1-1.6, Day -14 through Day -1). During Run-in, subjects will undergo HD at a reduced flow rate; have safety assessments; complete tests to assess cognitive function, quality of life, quality of sleep, and fatigue; and have blood samples collected for b2M and plasma proteomics. All subjects will have their HD flow rate adjusted to a maximum flow rate of 250 mL/minute, thus necessitating an increase in the overall length of dialysis time to approximately 4 hours.

Subjects who continue to meet eligibility requirements will be randomized at Visit 2 (Day 1) to one of two treatment arms: AKST1210 (the investigational treatment) or control (no column). The AKST1210 column will be connected in series before (upstream of) the HD dialyzer for the duration of each HD session, and an appropriate covering of either the AKST1210 column or control will be in place for blinding purposes. All randomized subjects will continue to undergo dialysis at the adjusted, maximum flow rate of 250 mL/minute at the extended dialysis time, similar to the Run-in Period. The subject, investigator, and outcomes assessor(s) will be blinded as to treatment (i.e., double-blind study).

There will be three (3) 4-week treatment periods, and subjects will receive 3 HD treatments with AKST1210 or control per week for 12 weeks. Subjects who may occasionally require an additional HD session per week would not receive the intervention on that additional day. Subjects randomized to the AKST1210 column will receive a 150 mL column (AKST1210 S-15) during Weeks 1 to 4 (Treatment Period 1). Subjects will then be evaluated for escalation to the 250 mL column (AKST1210 S-25) during Weeks 5 to 8 (Treatment Period 2) followed by evaluation for escalation to the 350 mL column (AKST1210 S-35) for Weeks 9 to 12 (Treatment Period 3). Subjects will be evaluated for escalation, de-escalation, or discontinuation based on specific criteria as specified in Protocol Appendix 17.1. Subjects will complete an EOS Visit during Week 14.

[figure not shown]

Figure 1. Study Schema

Subjects randomized to control will also receive 3 HD treatments per week for 12 weeks for blinding purposes with similar escalation, de-escalation, and discontinuation procedures (see Protocol Appendix 17.1).

During each Treatment Period, subjects will undergo tests to assess cognitive function, quality of life, quality of sleep, and fatigue, as well as collection of blood samples for b2M and plasma proteomics. AE assessments; review of concomitant medications; targeted physical examinations; monitoring of vital signs; and assessment of fluid status will occur at every treatment visit.

In the event of early termination of a subject who has been randomized and received at least 1 HD treatment, the EOS procedures will be performed unless the subject has withdrawn consent.

The overall duration of the study/recruitment period is approximately 12 months from study initiation (i.e., following consent of first subject) to study completion (i.e., last subject, last visit). Subject participation is expected to be approximately 16 to 20 weeks, unless prematurely discontinued.

4.2 Statistical Hypothesis

Because the primary objective of the study is safety and tolerability, the study is not designed to detect statistically significant differences between the AKST1210 column and control treatment on the efficacy endpoints. The statistical approach toward secondary efficacy endpoints will be primarily descriptive; within-subject changes from baseline for each treatment group will be evaluated by Wilcoxon signed-rank test. Hypothesis testing will be performed for the B2M data analysis and cognitive change based on Cogstate test battery, MoCA and PHQ-9. Please refer to the relevant sections below for details.

4.3 Sample Size Justification

Approximately 26 male and female subjects, ≥ 40 years of age on HD with ESRD-CI, will be enrolled. Assuming a drop-out rate of 20%, enrollment at this level will yield approximately 20 evaluable subjects. Subjects will be randomized in a 1:1 ratio consisting of 1 treatment arm (AKST1210) and 1 non-active, control arm; n=10 per group. The sample

size was chosen based on clinical considerations of an exploratory study designed to test safety and tolerability ([Thabane et al., 2010](#)).

The study is not statistically powered to detect differences in measures of clinical efficacy or biomarker endpoints. In addition, the proposed sample size may be sufficient to identify trends in efficacy endpoints that will be used to determine the appropriate sample size for subsequent studies.

4.4 Device/Control Used

The AKST1210 column is an extracorporeal column for adsorption of b2M from circulating blood, and it is placed in series with a hemodialyzer in an HD circuit. The control will consist of a covered surrogate object of similar size/shape as the AKST1210 column. The control will not in any way be in contact with circulating blood, as it sits external to the blood circuit. The control will be set up and draped in the same fashion as the AKST1210 column.

4.5. Randomization/Blinding and Unblinding

This is a randomized and double-blind study.

4.5.1 Randomization

Subjects will be randomized in a 1:1 ratio to either the AKST1210 column (the investigational treatment) or to control (no column). The study will be performed using a manual randomization process. Subjects will be randomized at Visit 2.1, after eligibility has been confirmed (including Day –14 to –1 Run-In). Subjects who discontinue or are unblinded may be replaced. Subjects who withdraw or are withdrawn during screening will be replaced. Replacement subjects will receive the same treatment as the original subjects. Subjects who have been unblinded will not be replaced.

4.5.2 Blinding and Unblinding

Unblinded site staff should prepare the dispensed AKST1210 column for the hemodialysis treatment according to the instructions for AKST1210 column operation. The subject and any blinded study personnel should not be permitted in the area during set up. After the column has been rinsed, primed, and prepared for treatment within the subject's hemodialysis circuit, the column should be held in place with a clamp. It should then be draped or wrapped with an opaque covering in order to ensure that the subject and blinded site staff remain blinded to the treatment assignment. After the AKST1210 column has been set up and draped appropriately, the subject should be brought to the treatment area to begin hemodialysis.

Subjects randomized to the control arm will not have an AKST1210 column used throughout their study participation. In place of an AKST1210 column, a control will be used to occupy the same space as an AKST1210 column and be held in place by an identical clamp used for the active treatment group. It will be draped or

wrapped with an opaque covering in order to ensure that the subject and blinded site staff remain blinded to the treatment assignment. The unblinded dialysis nurse/technician should set up the hemodialysis circuit as per their standard procedure and ensure that the control is attached to the hemodialysis machine in the same approximate location that an AKST1210 column would be placed and then route the hemodialysis lines through the control to simulate an in line AKST1210 column. Once the control has been set up and draped appropriately, the subject should be brought to the treatment area to begin hemodialysis. To maintain the blind, the control should be examined as frequently as the AKST1210 column during subjects' dialysis sessions.

To maintain the overall quality and legitimacy of the clinical trial, intentional unblinding of blinded staff prior to Database Lock at the site-level should not occur. If an exceptional circumstance requires blinded staff to be unblinded for adequate management of a subject, the investigator should discuss this with the unblinded Medical Monitor first. If unblinding is necessary, the subject's treatment assignment must NOT be disclosed to the subject and/or other blinded study personnel, blinded clinical research associates, or the Sponsor to the absolute extent possible.

All intentional and unintentional unblinding should be reported promptly to the unblinded clinical research associate, ideally within 24 hours of discovery. If accidental unblinding occurs, a root cause analysis may be performed, and preventative measures may be put in place to prevent further instances of unintentional, accidental unblinding.

4.6 Interim Analyses

Not applicable.

4.7 Study Assessment Time Points

The study consists of 6 protocol-specified visits which will be assessed as nominal visits from an analysis perspective:

- 1) Visit 1 Screening/Run-In: screening will be conducted at Days -42 to -14 and run-in will be conducted at Days -14 to -1.
- 2) Visit 2 Treatment Period 1 (Weeks 1- 4): randomization occurs on the same day as Day 1 and the first use of the device/control. Tolerability is monitored during each hemodialysis session. Evaluation for escalation, or discontinuation will be performed on Day 26.
- 3) Visit 3 Treatment Period 2 (Weeks 5- 8): Evaluation for de-escalation, escalation, or discontinuation will be performed on Day 54. Monitoring for de-escalation or discontinuation is assessed during each hemodialysis session.
- 4) Visit 4 Treatment Period 3 (Weeks 9- 12). Monitoring for de-escalation or discontinuation is assessed during each hemodialysis session.
- 5) Visit 5 End of Treatment (EOT) (Week 12, Day 82)

- 6) Visit 6 EOS (Week 14): In the event of early termination of a subject who has received at least 1 treatment, the end of study procedures will be performed unless the subject has withdrawn consent.

4.8 Schedule of Event

Refer to Protocol section 15.

4.9 Data Safety Monitoring Board (DSMB)

Safety oversight will be under the direction of a DSMB composed of individuals with the appropriate expertise, including ESRD and hemodialysis. Members of the DSMB will be independent from the study conduct and free of actual or perceived conflict of interest. The DSMB will meet at least quarterly (or more frequently as needed) to assess safety data. The DSMB will operate under the rules of an approved charter that will be written and reviewed at the organizational meeting of the DSMB. At this time, each data element that the DSMB needs to assess will be clearly defined. The DSMB will provide its input to Alkahest, Inc.

5 Statistical Methodology

5.1 General Considerations

This section presents the statistical approaches that are anticipated for the analysis of the study data. These approaches may at times require modifications due to unanticipated features of the data. Deviations from analyses summarized in this document will be noted in the CSR.

All statistical analyses will be performed using SAS® Version 9.4 or higher, unless otherwise noted. Data will be summarized using descriptive statistics, unless otherwise noted. Number of subjects (n) with non-missing values mean, median, standard deviation, minimum, and maximum will be summarized for continuous (quantitative) variables. Categorical (qualitative) variables will be summarized using frequencies and percentages of subjects who are in a particular category or each possible value. In general, the denominator for the percentage calculation will be based upon the total number of subjects in the study population for each treatment group, unless otherwise specified. The denominator for by-visit displays will be the number of subjects in the relevant study population with non-missing data at each visit. Presentations will be by treatment group (AKST1210 and Control) and Total, unless otherwise noted.

The minimum and maximum will be reported with the same degree of precision (i.e., the same number of decimal places) as the observed data. Measures of location (mean and median) will be reported to 1 degree precision more than the observed data and measures of spread (SD) will be reported to 2 degrees of precision more than the observed data.

Percentages will be presented to 1 decimal place, unless otherwise specified. Percentages will not be displayed when the numerator for a cell is 0.

Unless otherwise indicated, all statistical tests will be conducted at 0.05 significance level using 2-tailed tests, and P values will be reported. Corresponding 95% CIs will be presented for statistical tests.

In general, all summary tables will be supported by a relevant subject data listing including all subjects who are randomized. The listings will include all data collected, and will be sorted by subject ID, and actual visit date, as applicable, unless otherwise noted. The listing will also include the column size for each of the three treatment periods as applicable.

Study day 1 is the first day of HD treatment with AKST1210 or control. Study day is the day relative to the study day 1.

Baseline is the last non-missing value prior to the start of study hemodialysis during the run-in period V1.1, unless otherwise specified. Specifically:

- All the clinical labs, PE, and ECG will use Screening as the Baseline.
- Vital signs will use V1.1 prior to first study hemodialysis as the Baseline.
- PHQ-9 and MoCA will use the Screening Visit for Baseline.
- All the other questionnaires will use Visit 2.1 as the baseline

If values are missing at the defined baseline visit above an unscheduled value will be used, provided that the unscheduled assessment occurs prior to the start of the first hemodialysis during the Run-in period V1.1.

Change from baseline is the post-treatment value minus baseline value.

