4 STUDY DESIGN AND ENDPOINTS

4.1 DESCRIPTION OF THE STUDY DESIGN

This will be a randomized, double-blind study conducted at up to 5 sites in the US. Approximately 26 male and female subjects, \geq 40 years of age on HD with ESRD-CI, will be enrolled. Assuming a drop-out rate of 20%, enrollment at this level will yield approximately 20 evaluable subjects.

During Screening (Visit 1, Day -42 through Day -14), subjects and/or their legally authorized representative (LAR) will provide informed consent, and subjects will undergo screening assessments including provision of demographics and medical history, physical examination, 12-lead ECG, laboratory testing (including pregnancy testing if applicable), as well as tests to assess cognitive function and depression. A blood sample will also be obtained and sent to the site's local laboratory to determine baseline b2M concentration.

If the Visit 1 Screening eligibility criteria are met, subjects will commence the Run-in Period (Visits 1.1-1.6, Day -14 through Day -1). During Run-in, subjects will undergo HD at a reduced flow rate; have safety assessments; complete tests to assess cognitive function, quality of life, quality of sleep, and fatigue; and have blood samples collected for b2M and plasma proteomics. All subjects will have their HD flow rate adjusted to a maximum flow rate of 250 mL/minute, thus necessitating an increase in the overall length of dialysis time to approximately 4 hours.

Subjects who continue to meet eligibility requirements will be randomized at Visit 2 (Day 1) to one of two treatment arms: AKST1210 (the investigational treatment) or control (no column). The AKST1210 column will be connected in series before (upstream of) the HD dialyzer for the duration of each HD session, and an appropriate covering of either the AKST1210 column or control will be in place for blinding purposes. All randomized subjects will continue to undergo dialysis at the adjusted, maximum flow rate of 250 mL/minute at the extended dialysis time, similar to the Run-in Period. The subject, investigator, and outcomes assessor(s) will be blinded as to treatment (i.e., double-blind study).

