5.4.2 Baseline Disease Characteristics

Baseline disease characteristics will be summarized by treatment group and Total for the ITT population for the following:

- Baseline Historical IDH Rate (0,1,2,3,4)
- Dialysis Vintage
- Baseline b2M Level (V1.5)
- Baseline MoCA
- Baseline PHQ-9

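### SAP 5.1 sets lab and vital-sign baselines before the Run-in dialysis change, so on-treatment within-arm change combines the Run-in shift with any device effect; its missing-baseline rule also does not fit measures whose baseline is Visit 2.1

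*SAP*

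**What the plan says.** The baseline rules are in SAP 5.1 (General Considerations). The default is the last value before the V1.1 dialysis, with these specific rules:

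- Labs, physical examination, ECG: "All the clinical labs, PE, and ECG will use Screening as the Baseline".
- Vital signs: "Vital signs will use V1.1 prior to first study hemodialysis as the Baseline".
- MoCA and PHQ-9: Screening.
- Remaining instruments: "All the other questionnaires will use Visit 2.1 as the baseline". SAP 5.7.10 starts the post-baseline Cogstate time points at Visit 3, which places the Cogstate baseline at Visit 2.1 as well.
- b2M is handled in SAP 5.4.2 and 5.7.7, with its baseline inside Run-in: "Baseline b2M Level (V1.5)".

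If the baseline-visit value is missing, an unscheduled value may replace it, "provided that the unscheduled assessment occurs prior to the start of the first hemodialysis during the Run-in period V1.1". Change is defined thus: "Change from baseline is the post-treatment value minus baseline value".

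The timing is in Protocol 4.1. Screening is described as "During Screening (Visit 1, Day -42 through Day -14)". Run-in occupies Day -14 to Day -1, with six dialysis visits. At Run-in every subject's flow is capped at 250 mL/min, "thus necessitating an increase in the overall length of dialysis time to approximately 4 hours". Both arms keep this regimen during treatment. The device or control is first used at Visit 2.1 (Day 1). By the EOS visit, flow is back to standard of care (Protocol 15.1.5).

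SAP 5.8.6 and 5.8.7 plan observed values and change from baseline by visit for labs and vital signs, with optional shift tables for labs. Several of these outputs go to the DSMB.

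**The concern.** The plan changes two things in sequence: the dialysis regimen at V1.1, then the device at Visit 2.1. A baseline taken before the first change cannot isolate the second within an arm. The SAP elsewhere uses device start as its time origin: study day 1 is the first session with AKST1210 or control (5.1), and TEAEs count from device treatment (5.8.5). The lab and vital-sign baselines do not follow that origin.

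Change in labs and vital signs is a listed secondary endpoint, and no between-arm model is specified for it. The natural reading of the tables is therefore arm by arm. A movement in BUN, creatinine, electrolytes or blood pressure produced by slower, longer dialysis could be read as a device effect, or could mask one.

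The missing-baseline rule is a separate matter. For an instrument whose baseline visit is Day 1, it refuses a Run-in value taken days before first device use and accepts only one from before the regimen change.

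**Working it through.** The documents attach no figure to the baseline choice, so there is none to reproduce. The check compares the definitions with the schedules and then adds simple arithmetic on stated assumptions.

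**1. Timing** (SAP 5.1; Protocol 4.1, 15.1).
- Lab baseline: 14 to 42 days before Day 1.
- Vital-sign baseline: about 2 weeks, and six dialysis sessions, before Day 1.
- Cogstate, SF-36, PSQI, FACIT: Day 1.

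**2. What on-treatment change contains.** Let r be the mean shift caused by the Run-in regimen and d the device effect, both in SD units, with all other changes ignored. Neither is in the documents; r is assumed 0.2 to 0.8, and d is 0 or 0.5.

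- Screening/V1.1 baseline: active = r + d; control = r; difference = d.
- Pre-device baseline after Run-in: active = d; control = 0; difference = d.

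With the Screening/V1.1 baseline:
- d = 0 and r = 0.2, 0.5, 0.8: active 0.2, 0.5, 0.8; control the same; difference 0.
- d = 0.5 and r = 0.2, 0.5, 0.8: active 0.7, 1.0, 1.3; control 0.2, 0.5, 0.8; difference 0.5.

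The mixing is within-arm only. Randomization follows Run-in, so the shift cancels in expectation between arms.

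**3. Precision.** With equal variances, Var(change) = 2σ²(1 − ρ). Assume ρ of 0.5 to 0.7 between a Screening value and a later value, and 0.7 to 0.8 between a Day 1 value and a later value. The variance ratio is (1 − ρ_Screening)/(1 − ρ_Day 1):
- smallest: (1 − 0.7)/(1 − 0.7) = 1.0
- largest: (1 − 0.5)/(1 − 0.8) = 2.5

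At 10 per arm, the SE of the difference in mean change is √[(2/10) × 2(1 − ρ)]: 0.447 SD at ρ = 0.5, 0.346 at 0.7, 0.283 at 0.8.

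**4. Which measures have a later pre-device value.** Protocol 15.2 lists 37 non-serology lab lines: 8 hematology, 26 chemistry, 2 coagulation, 1 TSH. A Day 1 draw is scheduled for 8 + 14 + 2 = 24 of them (24/37 = 65%). The other 12 chemistry lines and TSH, 13 in all, are taken only at Screening and EOS, as is ECG. (The table is partly broken in extraction; SAP 5.8.6 confirms the 13.)

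Draw time matters. The rule that samples precede HD is given for Screening labs (Protocol 7.1.1.1.5) and for Run-in BUN, creatinine and aPTT (15.1.1, footnote 4). No such rule was found for Day 1 clinical labs. Blood pressure is recorded before every session, and other vital signs at the start of each visit (7.1.1.2.2).

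**5. The fallback.** A subject lacking the Visit 2.1 SF-36, for example, could be given only an unscheduled value from before V1.1. The schedules first list SF-36, PSQI and FACIT at Visit 2.1, so such a value is unlikely to exist. Since SAP 5.6 allows no imputation, the subject would then have no change score at any visit: 1 in 10, or 10%, of an arm at the planned evaluable size.

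**6. EOS.** Flow is again standard of care, so Screening-to-EOS (V1.1-to-EOS for vital signs) compares like regimens. If the shift fully reversed by then (an assumption), Day 1-to-EOS would carry −r in both arms, for example −0.5 SD when r = 0.5.

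**The case against.** The strongest reply is that the control arm exists for this purpose. Both arms share the Run-in and the regimen, tables are shown by arm, and within-arm change is not firm evidence of a device effect with any baseline. That stands, and it rules out reading the SAP rule as biasing the comparison of AKST1210 with control. It does not help someone reading the active-arm change or a shift table.

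A second reply is that the Run-in shift may already be displayed, because Day 1 is a scheduled visit after Screening. This stands in part. Mean shifts could be subtracted for subjects with complete data, but neither the SD of change from Day 1 nor the shift categories could be recovered. It is also unclear whether a pre-device Day 1 value counts, since the SAP defines change from a post-treatment value.

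Third, a reader might infer that a Day 1 pre-device value exists for every lab. The documents do not support that: 13 of 37 lab lines and ECG have no Day 1 value, and the Day 1 draw time is not stated.

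Fourth, a reader might infer that worsening anemia rests on a stale Screening hemoglobin. SAP 5.7.5 also allows comparison with the prior measurement and requires Hgb below 9 g/dL, so the dependence is partial.

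Fifth, moving every baseline to Day 1 would create the mirror problem at EOS. That is correct, and it narrows the remedy to on-treatment visits.

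Finally, the primary endpoint is TEAE and SAE incidence, and SAP 5.8.6 and 5.8.7 specify no test of change, so no planned test loses power.

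**Conclusion.** The point holds in a limited form. On-treatment within-arm change in labs and vital signs, and any lab shift tables, combine the Run-in shift with any device effect. The size of the mixing equals the Run-in shift, which the documents do not give; over an assumed 0.2 to 0.8 SD, all of it would appear in the active arm with no device effect. Between-arm contrasts remain unbiased.

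A reader might also infer a definite loss of precision. The documents give no correlations, and the assumed ranges run from no loss (ratio 1.0) to a ratio of 2.5, so precision is a secondary argument.

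The fallback rule is wrong as written and needs no assumption to show it: it sets a cut-off at V1.1 for instruments whose baseline is Visit 2.1. It affects only subjects missing that visit's value. Both matters merit correction; neither touches the primary endpoint.

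**What to change.** 1. **Fallback.** For each measure, accept the last non-missing value before the first AKST1210/control session at Visit 2.1. For Cogstate, state whether a Run-in familiarization assessment qualifies.
2. **On-treatment visits.** Compute change in vital signs, and in labs repeated in Run-in or on Day 1, from the last value documented as taken before the first AKST1210/control session. Use a Day 1 lab only if it is documented as drawn before HD; otherwise use the latest earlier value. Show the change from Screening (V1.1 for vital signs) to that value separately, as the Run-in effect.
3. **What stays.** Keep Screening as baseline for physical examination, ECG, MoCA, PHQ-9 and labs taken only at Screening and EOS. At the EOS visit, keep Screening-to-EOS change for labs and V1.1-to-EOS change for vital signs.

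The cost is SAP wording and derivation code, with no new data. Where a Day 1 draw time was not recorded, the rule falls back to the earlier value. The small downside is two reference points in the lab and vital-sign tables, which need clear labels.
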